### **Secondary Endpoints:**

Secondary clinical outcomes of interest will include but will not be limited to:

- Evaluation of PKG scores including BKS, DKS, PTT, FDS and PTI on healthy control subjects (non-PD; healthy control) to assess differences by age category.
  - PKG measurements will be recorded and compared across age ranges for subjects enrolled. Age categories of 18-40, from 40-59 years old, 60-79 years old, 80-90 years old and > 90 years old will be evaluated. This will provide a representative sample of subjects with early onset (<60 years), average age (60-79 years) and older subjects (80-90 years) with movement disorders.
- Comparison of PKG scores to standard PD assessments such as MDS-UPDRS, H&Y, PDQ39, FOG-Q, TETRAS, diaries
- Comparison of PKG scores to standard non-motor assessment such as NMSQuest
- Comparison of PKG scores to sleep assessments such as ESS and PDSS
- Comparison of PKG scores to MoCA
- Comparison of PKG scores to standard quality of life measurements such as EQ-5D
- Evaluation of product usability and satisfaction for PKG Watch, docking station and the PKG Portal

## 8. STATISTICS

Due to the nature of this research study, no formal hypothesis will be proposed, nor will a formal statistical analysis be conducted. Rather, this study will examine outcomes of each case and be descriptive in nature.

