## **1. PURPOSE**

The purpose of this study is to clinically validate new measures of the Personal KinetiGraph® (PKG®).

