#### In-Clinic Validation Testing

The Study PI will determine the required validation testing for each subject based upon the validation measure being tested. Subjects may receive video assessment of them walking or performing certain tasks while wearing the PKG Watch or PKG Watches (1 watch on each wrist). Subjects may also receive movement disorder related assessments such as Movement Disorders Unified Parkinson's Disease Rating Scale (MDS-UPDRS), Hoehn and Yahr scale (H&Y), Parkinson's Disease Questionnaire (PDQ-39), Non-Motor Questionnaire (NMSQuest), Freezing of Gait Questionnaire (FOG-Q), The Essential Tremor Rating Assessment Scale (TETRAS), Epworth Sleepiness Scale (ESS), Parkinson's Disease Sleep Scale (PDSS), the Montreal Cognitive Assessment (MoCA) and/ or other electronic patient/clinician/observer/performance reported outcomes (ePRO/ClinRO/ObsRO/PerfO) during this visit including EQ-5D, patient diaries. Each procedure and assessment will be explained to the subject upon enrollment into the study.

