## 7. STUDY ENDPOINTS

### **Primary Endpoint:**

Evaluation of new PKG assessments to be clinically validated including but not limited to gait/walking, Device Assisted Therapy readiness, Percent Time Bradykinesia (PTB), Percent Time Dyskinesia (PTD), fall prediction, disease progression and non-motor symptoms.

The primary endpoint evaluation for the validation of the new PKG measures will include standard calculations including correlation, point in time measurement compared to diaries and activity logs, change in PKG scores from beginning of recording to end of recording period, comparison of results between movement disorder patient recordings and those from healthy volunteer recordings to detect movement associated with movement disorder subjects compared to healthy volunteer subjects.

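### Clinical validation is the purpose and primary endpoint, but Section 8 excludes formal analysis and no interval or pass level is planned, so any validation criterion would be set after the data are seen

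*Combined protocol and SAP*

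**What the plan says.** Section 1 reads: "The purpose of this study is to clinically validate new measures" of the PKG. Section 7 gives the primary endpoint as "Evaluation of new PKG assessments to be clinically validated including but not limited to" seven named items: gait, Device Assisted Therapy readiness, PTB, PTD, fall prediction, disease progression and non-motor symptoms. It continues: "The primary endpoint evaluation for the validation of the new PKG measures will include standard calculations including correlation". The other calculations it names are comparison with diaries and activity logs, change over the recording, and patients against healthy volunteers.

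The secondary endpoints add candidate comparators without thresholds: "Comparison of PKG scores to standard PD assessments such as MDS-UPDRS, H&Y, PDQ39, FOG-Q, TETRAS, diaries", and "Comparison of PKG scores to standard non-motor assessment such as NMSQuest". On the choice of tests, Section 5 says: "The Study PI will determine the required validation testing for each subject based upon the validation measure being tested". It sends cohort-specific assessments and procedures, including video tasks, to the Manual of Operations, which was not supplied.

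Section 8 is two sentences long. It says that "no formal hypothesis will be proposed, nor will a formal statistical analysis be conducted", and that "this study will examine outcomes of each case and be descriptive in nature". Section 4 caps enrolment at 500 in total, patients and controls together, with no split by group or cohort.

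**The concern.** A descriptive analysis is legitimate in an observational post-market study, and a hypothesis test is not required. The difficulty is the pairing. The study sets out to validate measures, yet its statistics section rules out formal analysis and nothing else defines what validated means. Section 8 also fits poorly with Section 7, because a correlation or a patient-control comparison is a group quantity and not a case-by-case outcome.

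If a report later called a measure validated, a weak and a strong association would be equally compatible with the plan. The list of measures is open, several comparators are offered as examples, and tests are chosen subject by subject. Reference, metric and cut-off could therefore all be settled after the results were known.

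**Working it through.** **Is the gap filled elsewhere?** The one numeric sufficiency rule found is at least five full continuous days of recording (Table of Assessments). That concerns data completeness. The comparators in Sections 5 and 7 carry no threshold. Section 5 describes the Manual of Operations as covering assessments and procedures, not analysis.

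**Is there a figure to reproduce?** No. The 500 is a ceiling with no alpha, power, effect size or target precision behind it. What follows is illustration.

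**Assumptions (not in the documents).** Two patient numbers per measure:
- n = 35, from 500 / (7 measures × 2 groups) = 35.7, rounded down: separate cohorts.
- n = 250, half of 500: one set of patient recordings shared by all measures.

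Correlations and minimums are also assumed. All results use the Fisher z approximation.

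**Interval for an observed r of 0.5:** tanh(atanh(0.5) ± 1.96/√(n−3)), with atanh(0.5) = 0.549.
- n = 35: 0.549 ± 0.346, giving 0.20 to 0.71.
- n = 250: 0.549 ± 0.125, giving 0.40 to 0.59.

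**Chance of an observed r of at least 0.40:** 1 − Φ[(atanh(0.40) − atanh(ρ))·√(n−3)], with atanh(0.40) = 0.424 and atanh(0.2) = 0.203.

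| True ρ | n = 35 | n = 250 |
|---|---|---|
| 0.2 | 10.6% | 0.03% |
| 0.5 | 76% | 98% |

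For seven measures in separate cohorts of 35, all with true ρ = 0.2, the chance that at least one reaches 0.40 is 1 − (1 − 0.106)^7 = 54%.

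**Patients needed if the minimum applies to the lower confidence bound:** for 80% power at true ρ = 0.5 to clear 0.30, n = 3 + [(1.96 + 0.8416)/(atanh(0.5) − atanh(0.30))]² = 139.5, so 140. Seven separate cohorts of 140 would be 980 patients, above the ceiling of 500.

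**The case against.** The strongest reply is that the study is observational and openly descriptive, that Section 7 does name calculations and comparators, and that Section 12 promises only a contribution to objective evaluation of movement. Most of that stands. The plan is not empty, the absence of a test is no defect in itself, and references are only partly unspecified. None of it says what result would count as validated.

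A reader might go further and infer that the study can never support a validation claim. The documents do not support that. The Section 7 calculations remain, and intervals can be computed from the collected data. What cannot be supplied later is a criterion fixed before the results were seen.

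The Manual of Operations may hold more than Section 5 says. If it contains criteria, a cross-reference in Section 8 would settle that part.

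The numbers are fairly criticised as driven by assumptions. An equal 14-way split is stated nowhere, and correlation is only one of the four calculations. They show why an interval and a minimum matter; they do not predict this study's results.

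**Conclusion.** The point holds as a cheap improvement. This is a conflict between a stated rule in Section 8 and the study's own purpose, not merely missing detail. As planned, the study describes the measures, and any validation criterion would be post hoc.

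How much this matters depends on cohort size, which the documents leave open. With recordings shared across about 250 patients, a weak measure would rarely look moderate. With separate cohorts of about 35, it would do so about one time in nine per measure, and for at least one of seven about half the time. These figures rest on the assumed sizes, true correlations and 0.40 cut-off.

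**What to change.** Adopt one of two changes.

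**(a) Replace Section 8 with:**

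> Each primary-endpoint calculation will be reported with a 95% CI that treats the subject as the independent unit, with repeated time points and two-wrist recordings summarised per subject or handled as clustered; no hypothesis test is planned. Correlations with clinical scales will be estimated within the movement-disorder group, not pooled with controls. For each measure to be called clinically validated, the reference (from the assessments listed in Sections 5 or 7, including video), one primary metric and a sponsor-set minimum, stated as applying to the estimate or to the lower CI bound, will be recorded before that cohort's data are viewed. All measures examined will be reported; those with no recorded reference and minimum will be labelled exploratory.

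Cost: modest analysis work, with no added enrolment and no new type of assessment. Section 5 makes most assessments optional, so the chosen reference must be collected for every patient in that measure's cohort. Some measures may miss their minimum or be labelled exploratory.

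The sponsor should choose the kind of minimum knowingly. One on the lower bound is demanding, as the 140 patients per measure show. One on the estimate is easier to meet but carries the false-pass rates above when cohorts are small. Sharing recordings across measures, or claiming fewer measures, eases both problems.

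**(b) Keep Section 8** and replace the validation wording with describe or explore throughout: Sections 1, 4, 5 and 7 and the Table of Assessments. Changing Sections 1 and 7 alone would leave the conflict in the others. Cost: the validation claim is given up.

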## **9. INVESTIGATOR QUALIFICATIONS**

Physicians participating in this study must be able to conduct an assessment of clinical diagnosis to confirm subject either has a diagnosis of a movement disorder or is a healthy control subject. For the healthy control population, investigator will confirm the subject does not have other neurological disease(s) that would interfere with data collection and analysis.

## **10. INSTITUTIONAL REVIEW BOARD**

Each site is required to have Institutional Review Board (IRB) approval prior to starting this study and throughout the course of study conduct. Each site will maintain IRB correspondence including written initial and ongoing IRB approvals.

## **11. PROTOCOL DEVIATIONS**

A protocol deviation is defined as a circumstance in which the study investigator, site personnel or subject did not conduct the study according to the requirements of the study protocol.

Protocol deviations will be documented on the Protocol Deviation CRF and are to be reported per IRB requirements.

## **12. BENEFIT/RISK ANALYSIS**

Results from this study are expected to contribute to the objective evaluation of movement in subjects with PD against a standardized control dataset.

The PKG Movement Recording System and this study present no more than minimal risk to study subjects resulting in a minimal risk determination based on the PKG Movement Recording System, its use in this study, and the following criteria:

- Are not intended as an implant and present a potential for serious risk to the health, safety, or welfare of a subject;
- Are not purported or represented to be for use supporting or sustaining human life and presents a potential for serious risk to the health, safety, or welfare of a subject;
- Are not for a use of substantial importance in diagnosing, curing, mitigating, or treating disease, or otherwise preventing impairment of human health and presents a potential for serious risk to the health, safety, or welfare of a subject.

Adverse events and risks associated with this study are similar to those normally associated with standard clinical care of subjects with PD who wear the PKG watch; thus, additional

adverse events are not anticipated. Current product safety information, including contraindications, warnings, and precautions, are located in the Patient Instructions Manual and Clinical Interpretation Guide.

Although not anticipated, Unanticipated Adverse Device Effect (UADE) will be reported in accordance with 21 CFR 812.150 starting at the point of enrollment for all subjects enrolled into the study. A UADE is defined as any serious adverse effect on health or safety or any life-threatening problem or death caused by, or associated with, a device, if that effect, problem, or death was not previously identified in nature, severity, or degree of incidence in the investigational plan or application, or any other unanticipated serious problem associated with a device that relates to the rights, safety, or welfare of subjects.

Additionally, any complaints regarding any component of the PKG Movement Recording System will be reported to GK and processed per GK's standard post-market surveillance processes and any adverse events associated with the use of the PKG Movement Recording System will be summarized in the final report for this study.

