#### PKG Watch Administration for Extended Wear

After the Screening Visit, the study coordinator will order the required PKG System per subject enrolled as required. Upon receiving approval from site (this can only occur after a fully executed consent has been verified by the study coordinator), Global Kinetics (GK) Fulfillment Staff may contact the subject to explain PKG System use, and dispense the PKG System to the subject with a copy of the Patient Instruction Manual. The subject may contact the study site and/or GK Fulfillment Staff with any questions regarding the PKG System.

Concurrent with the PKG Watch wear for extended use, the subject may complete an activity journal of all movements throughout the day and a diary. The activity journal and diary will include recording of activities such as routine exercise like walking or jogging, outside of day-to-day living activities, sleep, medication times, falls, mood, symptoms. In addition, the subject may complete PKG questionnaires regarding their experience and usability of the product. The subject will complete the activity journal, diary and/or questionnaires via ePRO or sign and return the forms to the investigator using the provided stamped, addressed envelope via US mail.

For each cohort (PKG Score) that will be enrolled, Sponsor will indicate to clinical trial site and provide training on the procedures relevant to assessments associated with that cohort. Therefore, refer to the study Manual of Operations for detailed instructions for each assessment required, for each cohort that is being assessed, which will include procedures required for each cohort. Details on video recording and tasks to be completed (e.g., carrying a jug of water) will be detailed in the Manual of Operations.

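### Adverse event reporting is tied to the device, so injuries during the study's own walking and carrying tasks need not be recorded or summarised

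*Combined protocol and SAP*

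**What the plan says.** Section 12 (Benefit/Risk Analysis) gives three routes by which a safety event can be reported.

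- **Unanticipated adverse device effects.** These are reported from enrollment. They must be serious and caused by or associated with a device; the closing limb of the definition is "any other unanticipated serious problem associated with a device that relates to the rights, safety, or welfare of subjects".
- **Complaints.** These concern components of the PKG System and go to the sponsor's post-market process.
- **Final report.** The commitment is that "any adverse events associated with the use of the PKG Movement Recording System will be summarized in the final report for this study".

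On risk, Section 12 states that "The PKG Movement Recording System and this study present no more than minimal risk to study subjects". It then describes the study's adverse events and risks as "similar to those normally associated with standard clinical care of subjects with PD who wear the PKG watch", and expects no additional ones.

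The study procedures are in Section 5. Under In-Clinic Validation Testing, "Subjects may receive video assessment of them walking or performing certain tasks while wearing the PKG Watch or PKG Watches". Under PKG Watch Administration for Extended Wear, "Details on video recording and tasks to be completed (e.g., carrying a jug of water) will be detailed in the Manual of Operations". Sections 4 and 5 admit subjects with any movement disorder, as well as healthy controls.

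**The concern.** The reporting rule follows the device, but part of the physical risk that this protocol adds comes from its procedures. A subject can be hurt while walking or carrying something for the camera although the watch works perfectly.

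The protocol itself treats mobility as relevant in this population. Section 2 lists postural instability among the main motor symptoms of PD. Section 7 names gait/walking and fall prediction among the measures to be validated, and plans age categories of 80-90 and over 90.

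At stake is how the final report can be read. A statement that few or no adverse events occurred would appear to bear out the minimal-risk determination, but the reader could not tell whether task-related injuries had been looked for, or whether the sites had applied the same rule.

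**Working it through.** No arithmetic applies: the documents state no adverse event rate, no safety sample size and no safety hypothesis. The check is to trace one event through the text. Suppose a subject stumbles during a filmed carrying task and is injured, the watch has not malfunctioned, and the task was done as instructed.

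**Step 1: the three routes in Section 12**

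- Unanticipated adverse device effect: needs seriousness, unexpectedness and a link to the device. A minor injury fails the first test. A serious one qualifies only if someone judges it device-associated.
- Complaint: needs dissatisfaction with a component of the system. There is none.
- Final-report summary: needs an association with use of the system. The term is not defined. The watch was on the wrist, so one investigator may say yes; it played no part in the stumble, so another may say no.

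**Step 2: other places where the event might be caught**

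- Table of Assessments (Section 4): it has no adverse event row.
- Follow-up contact (Section 6): staff may ask about problems using the PKG System. The question is optional and confined to the device.
- Protocol Deviation form (Section 11): it covers departures from the protocol. A stumble in a correctly performed task is not one.
- Activity journal and diary (Section 5): the listed items include "sleep, medication times, falls, mood, symptoms". Completion is optional, it accompanies extended wear and not the in-clinic session, and nothing links it to the adverse event summary.

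Result: none of the three routes and none of the four other places requires this event to be recorded or summarised. One route leaves it to an undefined judgement, and a second does so only if the injury is serious.

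**Step 3: does the risk statement cover the tasks and the enrolled groups?**

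- Its stated scope includes the study as well as the system.
- Its three bulleted criteria (implant, life support, importance for diagnosis or treatment) are properties of a device, not of a walking or carrying task.
- Its comparator is PD subjects who wear the watch in standard care. Section 12 does not mention the filmed tasks, movement disorders other than PD, or healthy controls.

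**The case against.** The strongest reply is that the rule is looser than it looks. Association is a weaker test than causation. The tasks are done with the watch on, and Section 5 (PKG Watch for In-Clinic Wear) limits that wear to the required in-office testing, so the session is itself a use of the system. On that reading an investigator could count the injury, and could report a serious one as a device effect. This stands. A reader might infer that such injuries would never be counted; the documents do not support that. What they support is that counting is not required and depends on an undefined attribution.

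Second, a reader might infer that the risk statement describes only watch wear in PD care. It does not: it names the study and the system's use in it. PD care is the comparator. The criticism that remains is that equivalence to that comparator is asserted without assessing the tasks or the other groups.

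Third, the risk is mitigated. Section 5 excludes bedridden and wheelchair-confined subjects, regular users of gait aids, and those with an unstable or significant condition that would impair required assessments. Section 4 has a screening visit to confirm task ability. The tasks are optional and set by cohort. All of this lowers the chance of an injury; none of it says what is to be recorded if one happens.

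Fourth, the Manual of Operations and the case report forms are not available, and they may collect such events. That can be neither confirmed nor excluded. Even if they do, the Section 12 wording still sets what the final report must summarise.

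Finally, this is a post-market observational study of a cleared device with no safety endpoint. That is a fair reason to keep the point in proportion, but not to leave the wording as it is.

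**Conclusion.** The concern holds as a gap in required reporting. Section 12 limits the final-report summary by association with use of the PKG System, the other two routes are also tied to the device, and no other part of the documents obliges a site to record an injury from the study's own walking or carrying tasks. With up to 2 sites and up to 500 subjects, the same event could be classified differently at each site, and the resulting count would be hard to interpret. The risk paragraph equates study risk with PD care without assessing the tasks, movement disorders other than PD, or healthy controls.

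The size cannot be given in events. A reader might be tempted to project a number of missed falls, but the documents give no fall rate, no number of subjects doing the tasks and no split between groups; moreover, a fall without harm need not be an adverse event. The documents also do not show that the tasks provoke falls.

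The conclusion rests on the protocol text alone, with the Manual of Operations and case report forms unseen. No primary or secondary endpoint changes. The change is worth making because it is cheap and makes the safety statement interpretable.

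**What to change.** 1. Replace the final-report commitment at the end of Section 12 with wording such as: *Adverse events associated with use of the PKG System, or occurring during study-required in-clinic tests and tasks, will be recorded and summarised in the final report by relation (device or procedure) and by subject group.*
2. Add an adverse event row to the Table of Assessments in Section 4.
3. Extend the risk paragraph in Section 12 to mention the in-clinic tasks and every enrolled group: PD, other movement disorders and healthy controls.

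Cost: a short protocol amendment and one case report form entry, completed by staff already present at the visit. A few more events may be reported. No extra visit or subject is needed.
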